5.8.1.10. Adverse Events Leading to Treatment Discontinuation

Treatment discontinuation is collected on the End of Treatment eCRF. If the reason for treatment discontinuation is AE, the relevant AE number is also collected, and AEs recorded should match the cases on the AE eCRF where Action Taken is *Drug Withdrawn*. In the event of disagreement between these data sources, AE tables/listing will present data from the AE eCRF and disposition tables will present data from the End of Treatment eCRF. Given study treatment is a single dose, the incidence of AEs leading to treatment discontinuation is expected to be none/minimal.

5.8.1.11. Adverse Events Leading to Study Discontinuation

Study discontinuation is collected on the End of Study eCRF. *Adverse Event* is not collected as a possible reason for study discontinuation because the study only involves one dose of study drug, and the remainder of the study collects follow-up data (though an AE may lead to treatment discontinuation which the leads the participant/investigator to remove the participant from study). Therefore, no incidence table for TEAE leading to study discontinuation will be provided.

5.8.2. Death and Survival Status

Death status may derive from the Adverse Event, Survival Status, End of Treatment, or End of Study eCRFs. In each case, details are collected on the Death eCRF. In the event of data inconsistency, the Death eCRF data will be used. The number and percentage (based on the Safety Set) of participants who died will be summarized for primary cause of death (COVID-19,

Other Adverse Event, Unknown) and whether COVID-19 or COVID-19 complications contributed to the death by treatment group. Percentages of primary cause of death and whether COVID-19 contributed to the death will be based on the number of participants who died. A summary of AEs leading to death will also be provided by SOC and PT for the Safety Set.

A listing of death details as well as a listing of survival status for participants who discontinued the study early will also be provided.

5.8.3. Clinical Laboratory Evaluations

Blood samples for safety laboratory assessments (hematology, serum chemistry, and coagulation) will be collected on the days specified in the Schedule of Events ([Appendix M](#)). Laboratory assessments will be performed by a central laboratory and results will be graded at the laboratory according to DAIDS criteria, if applicable.

Descriptive statistics (based on SI units) for clinical laboratory test results (hematology, serum chemistry and coagulation) will be presented by treatment group and time point assessed. Descriptive statistics for the change from baseline to each post-baseline time point for the laboratory parameters will also be summarized by treatment group. In addition, the number and percentage of participants with potentially clinically significant (PCS) laboratory parameters will be summarized for any time post-baseline and by time point assessed.

A shift table of the DAIDS toxicity grading from baseline to worst post-baseline will be provided. For tests with both high and low DAIDS toxicity criteria, shift will be summarized separately for the high and low direction. A PCS value is defined as any DAIDS grade 4 post-baseline or any increase of 2 or more DAIDS grades post-baseline, except for PCS low creatinine clearance, which is defined as any DAIDS Grade 4 post-baseline or any DAIDS grade shift from 0 to 3.

Laboratory parameters not graded by DAIDs will be defined as PCS based on the criteria in [Appendix K](#). Refer to [Appendix B](#) for handling of unscheduled and multiple in-window values. All clinical laboratory values for participants with PCS will be provided in listings.

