4.1.1. Inclusion Criteria

Each participant must meet all of the following criteria to be enrolled in this study:

1. Age: Is an adult aged 18 years and above, or is an adolescent aged 12 to 17 years (inclusive) and weighing ≥ 40 kg at the time of screening

Note: Adolescent enrollment will open only upon sponsor communication to sites after iDMC review of safety data in adults, and only if permitted by the local health authority.

2. Has had a SARS-CoV-2 positive antigen test, or by RT-PCR, or other locally approved molecular diagnostic assay obtained within 5 days prior to randomization.

Note: A historical record of a positive result from a test conducted within 5 days prior to randomization is acceptable. SARS-CoV-2 antibody testing cannot be used for study eligibility.

3. Has had initial onset of one or more of the following self-reported COVID-19-related signs or symptoms within 5 days prior to randomization:

- measured temperature ≥ 38 °C (100.4 °F)
- subjective fever (feeling hot or feverish)
- chills (shivering)
- cough
- sore throat
- congestion (stuffy or runny nose)
- shortness of breath or difficulty breathing with exertion worse than usual
- muscle or body aches
- fatigue (low energy or tiredness)
- headache

- k. loss of taste or smell
- l. nausea or vomiting
- m. diarrhea

4. Has mild or moderate COVID-19 (per Section 2.2.2) with one or more of the following COVID-19-related signs or symptoms on the day of randomization:

- a. measured temperature ≥ 38 °C (100.4 °F)
- b. subjective fever (feeling hot or feverish)
- c. chills (shivering)
- d. cough
- e. sore throat
- f. congestion (stuffy or runny nose)
- g. shortness of breath or difficulty breathing with exertion worse than usual
- h. muscle or body aches
- i. fatigue (low energy or tiredness)
- j. headache
- k. loss of taste or smell
- l. nausea or vomiting
- m. diarrhea

5. Is at high risk of disease progression defined as:

- a. Age ≥ 55 years
- b. Age 18 to <55 years with one or more preexisting medical conditions as follows
 - i. Obesity (body mass index [BMI] ≥ 30 kg/m²)
 - ii. Diabetes (Type 1 or Type 2)
 - iii. Chronic kidney disease (eGFR calculated by Modification of Diet in Renal Disease [MDRD] of 59 mL/min/1.73 m² or less, including end-stage renal disease on hemodialysis)
 - iv. Chronic lung disease (emphysema/chronic obstructive pulmonary disease, chronic bronchitis, interstitial lung disease [including idiopathic pulmonary fibrosis], or cystic fibrosis)

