7.11. Safety Analyses

All AEs will be coded using the latest version of MedDRA. Safety summaries will be presented through Day 29 and overall.

A TEAE is defined as any AE that has an onset during or after the administration of study drug through the Month 14 visit, or any preexisting condition that has worsened during or after the administration of study drug through the Month 14 Visit. Because solicited AEs are expected to occur after the administration of study drug all solicited AEs will be considered TEAEs.

The incidence of TEAEs (including solicited ISRs), SAEs, TEAEs related to study drug, SAEs related to study drug, TEAEs leading to study drug discontinuation, AESIs, and MAAEs will be summarized by MedDRA SOC, PT, and treatment group. The incidence of study drug related TEAEs (including solicited ISRs) will also be summarized by maximum severity by SOC, PT, and treatment group.

The incidence of solicited AEs (ISRs) will be summarized by maximum severity through Day 4. The maximum duration and time from injection to report of first onset of any solicited ISR will also be summarized.

For all analyses of AEs, if the same AE (based on PT) is reported for the same participant more than once, the AE is counted only once for the PT and at the highest severity and most-related relationship to study drug.

Descriptive statistics for clinical laboratory test results (hematology, serum chemistry, and coagulation) and vital signs will be presented by treatment group and time point assessed. Descriptive statistics for the change from baseline to each post-baseline time point for the laboratory and vital sign parameters will be summarized by treatment group. In addition, treatment-emergent potentially clinically significant (PCS) laboratory parameters will be summarized in shift tables from baseline to each post-baseline time point assessed. The number and percentage of participants with a PCS vital sign will be summarized by treatment group for each time point assessed. PCS values will be defined in the SAP.

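### SAP 5.8.3 counts an unchanged pre-dose Grade 4 laboratory value as potentially clinically significant (PCS), although protocol 7.11 asks for treatment-emergent PCS values

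*SAP*

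**What the plan says.** Protocol 7.11 (Safety Analyses) commits to this display: "treatment-emergent potentially clinically significant (PCS) laboratory parameters will be summarized in shift tables from baseline to each post-baseline time point assessed". It leaves the thresholds to the SAP: "PCS values will be defined in the SAP".

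SAP 5.8.3 (Clinical Laboratory Evaluations) supplies the rule: "A PCS value is defined as any DAIDS grade 4 post-baseline or any increase of 2 or more DAIDS grades post-baseline". Low creatinine clearance has its own rule, "which is defined as any DAIDS Grade 4 post-baseline or any DAIDS grade shift from 0 to 3". The number and percentage of participants with PCS values "will be summarized for any time post-baseline and by time point assessed". The same section also promises: "A shift table of the DAIDS toxicity grading from baseline to worst post-baseline will be provided". High and low directions are shifted separately for tests graded both ways. Change-from-baseline summaries are planned, as are listings of all laboratory values for participants with PCS.

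Tests without DAIDS grades use the limits in SAP Appendix K. Most are multiples of the upper or lower limit of normal (urea nitrogen is PCS above 1.3 x ULN); only low hematocrit is set against the participant's baseline.

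SAP Section 1 gives the SAP precedence over the protocol where methods differ. SAP Section 7 states that nothing in the protocol's analyses has changed.

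**The concern.** The Grade 4 limb has no condition on the baseline grade. A participant at Grade 4 before the injection and still at Grade 4 afterwards has not worsened, yet enters the any-time PCS count. The same person can also be counted at each scheduled post-baseline laboratory visit (Days 7, 29 and 90 and Month 6). That is not treatment-emergent in any ordinary sense, so the SAP drops a condition that the protocol sets while declaring no change.

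Such participants may be enrolled. Inclusion criterion 5b iii admits chronic kidney disease, "including end-stage renal disease on hemodialysis". Whether they would be DAIDS Grade 4 on creatinine clearance at baseline is an assumption, because the documents do not reproduce the laboratory thresholds.

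At stake is how the PCS table reads. Unchanged disease would sit in the same cell as new Grade 4 abnormalities, and the relative excess in one arm would look smaller than it is.

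**Working it through.** The plan states no PCS rate, count or test, so there is no figure of its own to reproduce. The check has three parts.

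**1. Which cases does the rule misclassify?** Take grades 0 to 4 at baseline and post-baseline, in one direction, giving 5 x 5 = 25 pairs.

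- Post-baseline Grade 4 from baseline 0, 1 or 2 is a rise of 4, 3 or 2 grades, which the two-grade limb already catches.
- From baseline 3 it is a rise of 1. Only the Grade 4 limb catches it, and rightly, because the value worsened.
- From baseline 4 the rise is 0. Only the Grade 4 limb catches it, and nothing worsened.

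Adding a requirement that baseline be below Grade 4 changes exactly one pair of 25, the 4-to-4 pair. The creatinine clearance rule gives the same answer: only 4-to-4 changes.

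**2. What does that do to the counts?** Let g be the share of each arm at Grade 4 at baseline and throughout, and let a (ADG20) and p (placebo) be the new-onset PCS rates among the rest.

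- SAP rule: ADG20 = g + (1 - g)a; placebo = g + (1 - g)p.
- Baseline-conditioned rule: ADG20 = (1 - g)a; placebo = (1 - g)p.
- The difference is (1 - g)(a - p) under both rules, because g cancels.
- The ratio is a/p under the conditioned rule and is pulled toward 1 under the SAP rule.

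From the documents: 399 randomized 1:1, so about 200 per arm (the number dosed is not given). Assumed: g from 0% to 5%, equal in both arms and fully persistent; p = 2%; a = 4% or 6%.

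For a = 4%, p = 2%, g = 2%: ADG20 = 0.02 + 0.98 x 0.04 = 5.92%; placebo = 0.02 + 0.98 x 0.02 = 3.96%; ratio 1.49; difference 1.96 points. Under the conditioned rule: 3.92% versus 1.96%; ratio 2.00; difference 1.96 points.

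| g | Ratio, 4% v 2%: SAP / conditioned | Ratio, 6% v 2%: SAP / conditioned | Difference, 6% v 2% (both rules) | Power, 6% v 2%: SAP / conditioned |
|---|---|---|---|---|
| 0% | 2.00 / 2.00 | 3.00 / 3.00 | 4.00 points | 53% / 53% |
| 1% | 1.66 / 2.00 | 2.33 / 3.00 | 3.96 points | 45% / 53% |
| 2% | 1.49 / 2.00 | 1.99 / 3.00 | 3.92 points | 38% / 52% |
| 5% | 1.28 / 2.00 | 1.55 / 3.00 | 3.80 points | 27% / 51% |

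The power columns (200 per arm, two-sided 0.05) only gauge precision; the plan has no test of PCS rates.

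**3. Where else is the distinction visible?** For DAIDS-graded tests, the shift table from baseline to worst grade has a separate 4-to-4 cell. That table does not cover the Appendix K tests, and it runs to the worst value, so the by-visit PCS counts have no matching shift display. For Appendix K tests, a participant beyond an absolute limit at baseline can be recognised only from change-from-baseline summaries and listings. Elsewhere the SAP does handle this: Appendix K takes baseline into account for temperature, respiratory rate and heart rate.

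**The case against.** Much of the objection stands.

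- **The reporting as a whole does not mislead.** The section that defines PCS also plans the shift table, change-from-baseline summaries and listings. A careful reader can see that a Grade 4 value predates dosing.
- **PCS is not shown to be the main laboratory display.** A reader might infer that it is. The laboratory safety endpoint is change from baseline (Protocol Table 2-1, SAP Table 1), and SAP 5.8.3 introduces the PCS counts as an addition.
- **The comparison between arms is not biased in absolute terms.** A reader might infer that the treatment comparison as such is diluted. The planned output is a number and percentage per arm, with no ratio and no test, and the expected difference is the same under both rules.
- **The size is assumed throughout.** No baseline Grade 4 frequency is given, and exclusion criterion 9 may keep out some of the sickest patients.
- **A conservative screen that flags every Grade 4 is defensible.** A careless correction could do harm. It might drop participants from a listing that depends on PCS status, or exclude someone who moves from a low Grade 4 to a high Grade 4.

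One part does not stand. The protocol synopsis describes PCS summaries without the word treatment-emergent, and Section 7.11 hands the definition to the SAP. The synopsis merely omits the condition, and delegating the thresholds does not cancel a condition that Section 7.11 itself sets.

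**Conclusion.** The point holds as a minor mismatch between the SAP rule and the protocol. The mismatch follows from the texts alone and needs no assumption: the SAP rule counts 4-to-4 participants as PCS, protocol 7.11 asks for treatment-emergent values, and SAP Section 7 declares no change.

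The consequence is confined to the descriptive PCS counts. With baseline Grade 4 equally frequent in both arms and persistent, both percentages rise by about that frequency, the ratio moves toward 1 and precision falls, while the expected difference is essentially unchanged. Under the assumed rates, 1% to 2% baseline Grade 4 takes a ratio of 2.00 to between 1.66 and 1.49. If nobody is at Grade 4 at baseline, nothing changes. No efficacy result or error rate is touched.

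The documents do not support the stronger inference that prevalent disease will pass through the laboratory reporting as a drug signal, because the shift table isolates it for DAIDS-graded tests.

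**What to change.** In SAP 5.8.3, define the Grade 4 limb as a post-baseline Grade 4 with a baseline grade below 4, or missing, in the same direction (high or low) for that test. Put the same condition on the Grade 4 limb for creatinine clearance. Leave the two-grade limb, the 0-to-3 creatinine clearance shift and the shift table as they are.

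Report 4-to-4 participants on a separate line labelled as already Grade 4 at baseline, and state that they stay in the listing of all laboratory values.

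For Appendix K tests with absolute limits, such as urea nitrogen, show participants already beyond the limit at baseline on a separate line. Do not remove them: these tests have no grades, so a blanket exclusion could hide real worsening beyond the limit.

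The cost is one extra table line and one programming condition. Baseline grades are already needed for the shift table. The PCS count then agrees with the treatment-emergent condition in protocol 7.11.

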5.8.3.1. Hematology

The following hematology parameters (CBC with differential) will be assessed per the Schedule of Events ([Appendix M](#)):

- Hemoglobin
- Hematocrit
- Erythrocyte count
- Mean cell volume
- Mean cell hemoglobin
- Mean cell hemoglobin concentration
- Leukocyte (white blood cell) count
- Neutrophils

- Lymphocytes
- Monocytes
- Eosinophils
- Basophils
- Platelets

5.8.3.2. Serum Chemistry

The following serum chemistry parameters will be assessed per the Schedule of Events ([Appendix M](#)):

- Glucose, non-fasting
- Calcium
- Albumin
- Total protein
- Sodium
- Potassium
- Bicarbonate
- Chloride
- Urea nitrogen
- Creatinine (and calculated eGFR)
- Alkaline phosphatase (ALP)
- Alanine aminotransferase (ALT)
- Aspartate aminotransferase (AST)
- Total bilirubin
- Human chorionic gonadotropin (hCG) for females

5.8.3.3. Coagulation

The following coagulation parameters will be assessed per the Schedule of Events ([Appendix M](#)):

- Prothrombin time (PT)/International Normalized Ratio (INR)
- Partial thromboplastin time (PTT)/activated Partial thromboplastin time (aPTT)

5.8.4. Vital Sign Measurements

Vital signs, including temperature, heart rate, respiratory rate, seated blood pressure, and SpO₂ will be summarized using the site staff assessment.

Descriptive statistics for vital signs and for the change from baseline to each post-baseline time point will be presented by treatment group. The number and percentage of participants with a PCS vital sign parameter will be provided for any time post-baseline and separately for the time period of intensive monitoring post-study drug administration. PCS values are provided in [Appendix K](#). Refer to [Appendix B](#) for handling of unscheduled and multiple in-window values.

All vital sign data by participant will also be presented in listings separately for in-person visit and eDiary. Vital Sign listings will include participant recordings and will list data by visit, date and timepoint.

5.8.5. Other Safety Data

Pregnancy testing data will be provided in a listing for all female participants whose fertility status (as collected on the Screening Fertility Status eCRF) is *Child-Bearing Potential* or *Unknown*.

6. PHARMACOKINETIC ANALYSES

All PK listings, individual concentration-time profiles, PK tables and figures, and all statistical analyses will be presented using the PK analysis set.

6.1. Data Handling

Data rounding specifications for PK data are documented in the PK TLF shells. Handling of missing data is detailed in Section [4.1](#).

6.2. Serum Concentrations

Serial blood samples will be collected at the following time points (with collection window) for PK assessment:

- Day 1 at baseline (Predose)
- Day 7 (± 1 day), Day 29 (+5 days), Day 90 (± 14 days), Month 6 (± 30 days), Month 11 (± 30 days)
- Unscheduled

Individual serum concentrations of ADG20 will be presented in data listings and summarized separately using descriptive statistics (number of observations, arithmetic mean, SD, CV, geometric mean, geometric mean CV%, median, minimum, and maximum) by time point.

Individual serum concentrations will be plotted by actual time on both linear and semi-logarithmic scales. Mean (SD) serum concentrations will be plotted by part, treatment, nominal time on both linear and semi-logarithmic scales.

In addition, individual serum concentrations of ADG20 will be presented in data listings and summarized by ADA status (positive/negative). Individual and mean concentration plots will also be presented by ADA status (treatment emergent ADA positive/negative).

6.3. Serum Pharmacokinetic Parameters

Serum concentration-time data will be analyzed by non-compartmental analysis using Phoenix® WinNonlin® Version 8.0 or higher (Certara USA, Inc., Princeton, NJ). The PK parameters to be calculated for ADG20, where data permit, as listed in [Table 8](#).

Table 8: Calculated PK Parameters

Parameter	Definition
C_{\max}	Maximum observed concentration.
T_{\max}	Time of maximum observed concentration.
$AUC_{0-\text{last}}$	AUC from time 0 to the last measurable observed concentration (C_t), calculated using the linear trapezoidal rule.
$AUC_{0-\infty}$	AUC from time 0 extrapolated to infinity, calculated as $[AUC_{0-\text{last}} + (C_t / \lambda_z)]$.
$T_{1/2}$	Apparent terminal elimination half-life, calculated as: $\ln(2) / \lambda_z$.
CL/F	Apparent total body clearance, calculated as: Dose / $AUC_{0-\infty}$.
V_d/F	Apparent volume of distribution during the terminal phase (for IM dose), calculated as: Dose / $[\lambda_z \times AUC_{0-\infty}]$.

In addition to the PK parameters shown in [Table 8](#), which will be listed and summarized, the parameters in [Table 9](#) will also be listed to document the selection of data points used to estimate $T_{1/2}$ using non-compartmental procedures.

Table 9: PK Parameters for Data Selection

Parameter	Definition
λ_z	Apparent terminal elimination rate constant, where λ_z is the magnitude of the slope of the linear regression of the log concentration versus time profile during the terminal phase.
Number points	Number of data points used to estimate λ_z ; a minimum of 3 data points must be used, and C_{\max} must not be included.
λ_z lower	Lower bound used for the estimation of λ_z .
λ_z upper	Upper bound used for the estimation of λ_z .
Rsq (R2)	R2, the coefficient of determination (goodness of fit statistic); λ_z and all associated parameters will only be reported where $R2 \geq 0.80$.
%AUC _{ext}	Percentage of $AUC_{0-\infty}$ due to extrapolation; $AUC_{0-\infty}$, CL/F and V_d/F values will be flagged and excluded from summary statistics where $%AUC_{ext} > 20\%$.

Actual sampling times will be used for the estimation of all serum PK parameters, and all concentrations will be included in the analysis (including concentrations collected outside predefined collection windows).

Serum PK parameters will be presented in data listings and summarized separately using descriptive statistics (number of observations, arithmetic mean, SD, CV, geometric mean, geometric CV, median, minimum, and maximum) by part, treatment. T_{\max} will be summarized using number of observations, median, minimum, and maximum only.

In addition, serum PK parameters will be presented in data listings and summarized by ADA status (treatment emergent ADA positive/negative).

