1.1.2.1. Study ADG20-1-001

Study ADG20-1-001 is a first-in-human, Phase 1, randomized, double-blind, placebo-controlled, single ascending dose study conducted in the United States in healthy adult volunteers to evaluate the safety and PK of ADG20 (100 mg/mL formulation). To date, 24 participants across 3 dose levels (300 mg IM, 500 mg IV, and 600 mg IM) received ADG20 (8 per dose cohort) and 6 received placebo (2 per dose cohort). Dosing in these cohorts was initiated on 12-Feb-2021 and completed on 23-Mar-2021; follow-up is ongoing.

Preliminary findings from blinded data review with a minimum of 9 months of follow-up showed that no SAEs, AESIs (hypersensitivity reactions or infusion-related reactions), study drug-related AEs, or ISRs have been reported. The observed ADG20 PK appears to be dose proportional, with an estimated half-life of approximately 97 days based on linear regression of the Days 21, 90, and 180 PK timepoints from the 300 mg IM dose.

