3.4.3. PK and ADA Assessments

On Day 1, a blood sample for PK assessment will be collected prior to study drug administration. Blood samples for PK assessment will also be collected on Days 7, 29, 90, and at Month 6 and Month 11. Blood samples for determination of ADA (and neutralizing antibody) against ADG20 will be collected on Days 1, 29, and 90, and at Months 6 and 11.

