APPENDIX B. ANALYSIS VISIT WINDOWS

Assessments collected at scheduled or unscheduled visits will be mapped using the analysis visit windows listed in [Table 10](#). All diary data will be analyzed using the actual day. Refer also to Section [4.1](#).

Table 10: Analysis Windows

AVISIT	AVISITN	Range of Trial Day	Target Day	If more than one value, which value is used for analyses
Screening	1	Day -2 to 1		Last value prior to administration of study drug
Day 1	2	Day 1	Day 1	Day 1
Day 3	4	Day 2 to Day 4	Day 3	Nominal visit. If none exist, then closest to target day.
Day 5	6	Day 4 to Day 6	Day 5	Nominal visit. If none exist, then closest to target day.
Day 7	8	Day 6 to Day 8	Day 7	Nominal visit. If none exist, then closest to target day.
Day 11	12	Day 9 to Day 13	Day 11	Nominal visit. If none exist, then closest to target day.
Day 14	15	Day 12 to Day 16	Day 14	Nominal visit. If none exist, then closest to target day.
Day 21	22	Day 18 to Day 23	Day 21	Nominal visit. If none exist, then closest to target day.
Day 29	30	Day 24 to Day 34	Day 29	Nominal visit. If none exist, then closest to target day.
Day 60	31	Day 53 to Day 67	Day 60	Nominal visit. If none exist, then closest to target day.
Day 90	32	Day 76 to Day 104	Day 90	Nominal visit. If none exist, then closest to target day.
Month 6	33	Day 150 to Day 210	Day 180	Nominal visit. If none exist, then closest to target day.
Month 11	34	Day 300 to Day 360	Day 330	Nominal visit. If none exist, then closest to target day.
Month 14	35	Day 360 to Day 480	Day 420	Nominal visit. If none exist, then closest to target day.

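### Dropping AUC0-inf, CL/F and Vd/F from the summaries above 20% extrapolation makes inclusion depend on half-life, so these summaries describe faster eliminators than the T1/2 summary does

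*SAP*

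**What the plan says.** SAP Section 3.4.3 gives the post-dose schedule: "Blood samples for PK assessment will also be collected on Days 7, 29, 90, and at Month 6 and Month 11". There is no PK sample at Month 14. SAP Appendix B places Month 6 at "Day 150 to Day 210" (target Day 180) and Month 11 at "Day 300 to Day 360" (target Day 330).

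SAP Section 6.3 obtains AUC0-last as an area "calculated using the linear trapezoidal rule" up to the last measurable concentration. AUC0-inf adds the last concentration divided by lambda-z, and CL/F and Vd/F follow from AUC0-inf. For lambda-z, "a minimum of 3 data points must be used", Cmax may not be one of them, and R2 must be at least 0.80. Table 9 then says that AUC0-inf, CL/F and Vd/F "values will be flagged and excluded from summary statistics where" the extrapolated share exceeds 20%. The rule does not cover T1/2, Cmax, Tmax or AUC0-last.

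The half-life comes from Protocol Section 1.1.2.1, which reports for the Phase 1 study an "estimated half-life of approximately 97 days based on linear regression of the Days 21, 90, and 180 PK timepoints" after 300 mg IM.

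The PK parameters are secondary endpoints, as data permit (Protocol Table 2-1, SAP Table 1). Neither document plans a summary that includes the flagged values or a partial AUC over a common interval.

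**The concern.** The extrapolated share is set by the last sampling time and the participant's own half-life. A fixed limit of 20% therefore selects on elimination rate, from which CL/F, Vd/F and AUC0-inf are derived. Slow eliminators leave the summary, and most participants who miss Month 11 leave it unless they eliminate quickly.

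At stake is the reading of three named secondary PK parameters. The T1/2 row and the AUC0-inf, CL/F and Vd/F rows of one table would describe different participants, and a larger sample does not remove a selection of this kind. AUC0-last does not fill the gap because it ends at a different time in different participants: at a 97-day half-life it covers about 72% of the total AUC if it stops at Day 180 and about 91% if it stops at Day 330.

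**Working it through.** The documents state no expected extrapolated share and no expected number of exclusions, so there is no plan figure to reproduce.

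**Inputs from the documents.** Half-life 97 days (Protocol 1.1.2.1); Month 6 at Day 180, range 150-210, and Month 11 at Day 330, range 300-360 (SAP Appendix B); 20% limit (SAP Table 9).

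**Step 1: extrapolated share.** For a single-exponential decline, the share beyond the last sample is 2^(-t_last / T1/2). At 97 days:

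| Last sample | Share extrapolated |
|---|---|
| Day 90 | 52.6% |
| Day 150 | 34.2% |
| Day 180 | 27.6% |
| Day 210 | 22.3% |
| Day 300 | 11.7% |
| Day 330 | 9.5% |
| Day 360 | 7.6% |

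The share is above 20% throughout the Month 6 window and below it throughout the Month 11 window.

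**Step 2: half-life at which a participant is dropped.** Setting the share to 20% gives T1/2 = t_last × ln 2 / ln 5.
- Month 6 last: 77.5 days at Day 180 (65 at Day 150, 90 at Day 210).
- Month 11 last: 142 days at Day 330 (129 at Day 300, 155 at Day 360).

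As a check, the SAP's own rules (linear trapezoid, log-linear lambda-z on at least 3 points after Cmax) were applied to the planned sampling days, using a one-compartment model with an assumed absorption rate of 0.5/day. This gave about 28.1% and 9.5% extrapolated, with cut-offs of about 77 and 141 days.

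**Step 3: size, under assumptions.** These are not in the documents: half-life lognormal with geometric mean 97 days and CV 20-30%; 15% of participants with Month 6 as last sample and 85% with Month 11, all at target days.

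Let s = sqrt(ln(1 + CV²)), a1 = ln(142.1/97)/s and a2 = ln(77.5/97)/s. Then
- share kept K = 0.85 Φ(a1) + 0.15 Φ(a2)
- shift in mean log half-life among those kept = -s × [0.85 φ(a1) + 0.15 φ(a2)] / K

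For CV 25%: s = 0.246, a1 = 1.551, a2 = -0.910. K = 0.85 × 0.940 + 0.15 × 0.181 = 0.826. Shift = -0.246 × (0.85 × 0.120 + 0.15 × 0.264) / 0.826 = -0.042.

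Because log T1/2 is a constant plus log V minus log CL, a fraction q of its variance due to clearance (independent of volume) passes q × shift to log AUC0-inf and (1 - q) × shift to log Vd/F.

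| Half-life CV | Excluded | AUC0-inf low, all through clearance | AUC0-inf low, shared equally | AUC0-inf low, all through volume |
|---|---|---|---|---|
| 20% | 15.4% | 2.0% | 1.0% | 0% |
| 25% | 17.4% | 4.1% | 2.1% | 0% |
| 30% | 19.9% | 6.7% | 3.4% | 0% |

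CL/F is high by nearly the same percentages as AUC0-inf is low. Vd/F mirrors AUC0-inf: unchanged if all variation is through clearance, low by 1.0-3.4% if shared, and low by 2.0-6.7% if all is through volume.

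**Step 4: wider simulation.** With clearance CV 20-40%, volume CV 10-30%, 10% assay error and 0-30% missing Month 11 (all assumed), 62-83% of estimable participants without Month 11 were excluded, and 6-22% of those with it. Geometric mean AUC0-inf was 2-13% lower, and CL/F 2-15% higher, than in the same analysis without exclusion. With clearance CV 5% and volume CV 30%, the AUC0-inf shift was about 0.2%.

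**The case against.** A reader might infer that the rule simply understates exposure and overstates clearance. The documents do not support that as an unconditional statement. They give no between-participant variance for clearance or volume, and the split between the two decides whether AUC0-inf and CL/F move, or Vd/F, or both. That objection stands, and it is why the direction is stated conditionally here.

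The size also rests on assumptions. The 97 days is a preliminary healthy-volunteer estimate from a cohort in which 8 participants received ADG20. With a Month 11 sample, the typical participant is kept. If everyone had one, the Step 3 formula at CV 20% excludes only 2.7%, with AUC0-inf at most 1.3% low. At the low end, the linear trapezoid's own upward error of about 2-3% roughly offsets the shift, so the summary need not be low against the true AUC. The figures above are relative to the same analysis without exclusion.

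The plan already shows part of the problem. Individual values are listed, each parameter summary reports its number of observations (SAP 6.3), and Cmax, AUC0-last, T1/2 and concentrations by visit are summarised without this filter. A reader would see N fall between T1/2 and AUC0-inf, but not that those lost are the slower eliminators. The summaries are descriptive and feed no test. A separate PK analysis plan for Phase 2 is cited in Protocol 7.13 and SAP Appendix L but is not available here.

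Finally, the filter is prespecified, and caution about heavily extrapolated areas is reasonable. That supports keeping the flag. It does not make the retained subset representative.

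**Conclusion.** The point holds in conditional form and is a cheap improvement; the efficacy analyses are not affected. From the plan's own half-life and sampling days, the rule drops a typical participant without Month 11 and, among those with Month 11, participants with half-lives above about 142 days (129-155 over the window). T1/2 is therefore summarised in a different set of participants from AUC0-inf, CL/F and Vd/F. This part needs no assumption beyond the 97 days and a roughly exponential decline.

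The consequence depends on where the half-life variation comes from. At a half-life CV of 20-30% and 15% without Month 11, about 15-20% are excluded. The AUC0-inf shift then runs from 0% through about 1-3% to about 2-7%, according to whether the variation lies in volume, is shared equally, or lies in clearance; Vd/F moves in the complementary way.

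**What to change.** In SAP Table 9, keep the flag above 20%, but summarise AUC0-inf, CL/F and Vd/F twice: for all participants with an acceptable lambda-z fit, and for the unflagged subset.

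Add a partial AUC over one fixed interval that observed samples cover, for participants with a Month 6 or later sample. Day 150, the start of the Month 6 window, is a suitable end point, with the concentration there interpolated from actual sampling times. Day 180 would not serve: a participant sampled between Days 150 and 179 with no later sample would need extrapolation to reach it. State the interpolation rule, because a straight line from Day 90 to Month 11 lies above an exponential decline when Month 6 is missed.

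The cost is SAP wording and a few summary rows from data already collected. The all-participant summary will contain less precise extrapolated values. It will also still omit anyone who fails the 3-point or R2 rule, such as a participant without Month 11 whose Cmax falls at Day 29, who has only two later points.
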